## 2. SYNOPSIS

STUDY DRUG:	Mirabegron 25-50 mg daily
STUDY TITLE:	A pilot study of Mirabegron and behavioral modification including pelvic floor exercise for overactive bladder in Parkinson Disease (PD)
STUDY OVERVIEW:	
This study is a randomized 1:1 placebo-controlled 10-week study of mirabegron as add-on therapy to an educational intervention of behavioral modification including pelvic floor exercise (PFE) in a cohort of 40 PD subjects over the age of 30 with overactive bladder (OAB). Active drug will be mirabegron 25 mg daily with up-titration to 50 mg daily after 5 weeks. Subjects will be enrolled based on response to an overactive bladder questionnaire at baseline –visit 2. Voiding diaries (72-hr) will be utilized following the screening visit and phone visits 1 and 2. In the diaries, subjects will record the time of each micturition and/or urgency episode, urine volume with each void, any episode of incontinence, and the severity of urgency (according to the scale used in the Overactive Bladder Symptom Composite Score, OAB-SCS): 1 = no urgency (normal voiding); 2 = mild (could postpone voiding for as long as necessary without fear of incontinence); 3 = moderate (could postpone voiding for a short while without fear of leakage); 4= severe (could not postpone, had to rush to the toilet); 5= urgency incontinence (could not make it to the toilet without some leakage).
 
Diaries will also record pelvic floor exercises. Primary outcome will be change in mean daily OAB-SCS (summation of all urgency scores recorded at all voids throughout the 72hr diary recording averaged over 3 days), visit 4 vs. baseline.

STUDY HYPOTHESIS:	Treatment with Mirabegron will improve urinary urgency control beyond that achieved with pelvic floor exercises alone.
STUDY SUBJECTS:	40 subjects with Parkinson disease and OAB complaints.
DESIGN:	Multiple-dose, randomized, placebo-controlled prospective, single-site, investigator-initiated trial.
DURATION OF STUDY:	10 weeks (active treatment)
TREATMENT REGIMEN:	
Group A will receive Mirabegron 25mg daily; at visit 3, those who up-titrate will receive two 25mg tablets
 
Group B will receive placebo; at visit 3, those who up-titrate will receive two placebo tablets
 
Group A and B will receive the same baseline education in pelvic floor exercise based on viewing of an instructional PowerPoint presentation plus take-home printed material.


TREATMENT PERIOD:
	
Treatment Period:
 
 
• Screening = Screening to baseline (1-2 weeks)
 
• Active period = Baseline to final visit (10-12 weeks)
 
 
Number of Visits: 4 (screening, randomization, visit 3 (titration) and visit 4 (final))
 
Two phone visits. Phone visit 1 at 7-14 days post visit 1. Phone visit 2 at 70-74 days post visit 2


INCLUSION AND EXCLUSION CRITERIA:
	
Inclusion Criteria
 
 
• Diagnosis of PD by UK brain bank criteria
 
• Age <math>\geq</math> 30 years old
 
• No change in PD medications during the 4 weeks preceding screening, with no dose changes during the study, except that PRN (as needed) doses of carbidopa/levodopa will be allowed to address periodic worsening of parkinsonian symptoms.
 
• Patient willing and able to complete micturition diary
 
• Urinary urgency (<math>\geq</math> 8 entries of bladder urgency score <math>\geq</math> 2) in 72hr voiding diary during screening period
 
• Micturition frequency <math>\geq</math> 8 / 24hr or incontinence <math>\geq</math> 2 episodes in 72hr voiding diary during screening period
 
• Use of other medication that could influence bladder function, other than those specifically prohibited (see below), will be permitted as long as the dose is stable for 4 weeks preceding screening, with no dose changes during the study.
 
• Patient expects to have valid health insurance for the duration of the study period
 
 
Exclusion Criteria
 
 
• Women who are breast-feeding, pregnant or have potential to become pregnant during the course of the study (fertile and unwilling/unable to use effective contraceptive measures).
 
• Cognitive deficits that in the opinion of the investigator would interfere with the subject's ability to give informed consent or perform study testing.
 
• Screening blood pressure > 165 systolic or 100 diastolic
 
• Heart rate > 100
 
• History of allergy to Mirabegron.
 
• Screening post-void residual > 200ml
 
• Evidence of urinary tract infection at screening
 
• History of chronic inflammation such as interstitial cystitis, bladder stones, previous pelvic radiation therapy, or previous or current malignant disease of the pelvic organs
 
• Intravesical botulinum toxin treatment within the previous six
 

	
months of screening.
 
 
• Presence of Interstim device
 
• Use of indwelling catheter or self-catheterization
 
• Concurrent use of thioridizine, flecainide, propafenone, or Digoxin
 
• Concurrent use of warfarin (Coumadin)
 
• Use of one of the anti-cholinergic bladder medications specified below within 14 days of the screening visit. Subjects who have used one of these medications in the past but discontinued it at least 14 days prior to the screening visit can be enrolled.
 
• Screening estimated glomerular filtration rate (eGFR) < 60, AST or ALT > 2x upper limit of normal
 
• Any other serious and/or unstable medical condition
 
• Participation in other drug studies or use of other investigational drugs within 30 days prior to Screening Visit.
 

PROHIBITED MEDICATIONS:
	
Warfarin (Coumadin)                  Thioridizine                  Flecainide                  Propafenone                  Digoxin                  Intravesical botulinum toxin                  Anticholinergic bladder agents                      Darifenacin (Enablex)                      Fesoteridine (Toviaz)                      Flavoxate (Urispas)                      Oxybutynin (Ditropan, Ditropan XL, Oxytrol, Uromax, Apo-Oxybutynin, Riva-Oxybutynin, Cystrin)                      Solifenacin (Vesicare)                      Tolterodine (Detrol, Detrol LA, Detrusitol, Unidet)                      Trospium (Sanctura, Sanctura XR)

LOCATION:
	
Booth Gardner Parkinson’s Care Center                  EvergreenHealth                  Suite 300                  [name]                  [name], United States                  Ph: [contact] [contact]

NO. OF SUBJECTS:
	
N= 40. This will include 20 subjects taking Mirabegron and 20 subjects taking placebo.


EFFICACY          (Outcome measures):
	
Primary Outcome Measure          Change in mean daily OAB-SCS, visit 4 vs. baseline.
 
Secondary Outcome Measures based on voiding diary
 
 
• Change in mean daily OAB-SCS, Visit 3 vs. baseline
 
• Mean number of micturitions per 24 hours, Visit 3 and Visit 4 vs. baseline
 
• Mean number of incontinence episodes per 24 hours, Visit 3 and Visit 4 vs. baseline
 
• Mean volume voided per micturition, Visit 3 and Visit 4 vs. baseline
 
 
Secondary Outcome Measures based on clinic visits
 
 
• Overactive Bladder questionnaire symptom severity scale (OAB-q), Visit 3 and Visit 4 vs. baseline
 
• Non-Motor Symptoms Scale (NMSS), which includes questions about cognition, psychosis, and constipation, in addition to urinary symptoms; Visit 3 and Visit 4 vs. baseline.
 
• Patient Perception of Bladder Condition at Visit 3 and Visit 4 vs. baseline
 
• Subject's Global Impression of Change at Visit 3 and Visit 4 vs. baseline
 

STATISTICAL METHODS:
	
Demographics and baseline disease characteristics, including age, gender, duration of disease, modified Hoehn and Yahr stage, MDS-UPDRS motor (part 3) subscore, PD medications including levodopa-equivalent daily dose (LEDD), and other medications for OAB will be compared between study groups.
 
LEDD will be calculated according to standardized formulae (Tomlinson 2010).
 
Analysis of primary and secondary outcome measures will include:
 
 
• Summary statistics (n, mean, standard deviation, median, minimum and maximum) at baseline, visit 3 and visit 4 by treatment.
 
• Summary of % change from baseline to visit 3 and 4.
 
• Significance testing
 
 
The primary time points for all comparative measures will be Baseline Visit (Visit 2), Titration Visit (Visit 3) and Final Visit (Visit 4). Outcome measures will be compared between groups using analysis of covariance (ANCOVA) or other method as deemed appropriate by the consulting statistician. Demonstration of superiority will depend on achieving statistical significance for the primary endpoint. Level of significance will be defined as <math>p = 0.05</math>. All statistical tests will be two-sided. Statistical

	
assistance will be provided by a statistician consultant whose company is contracted with EvergreenHealth and whose services we have used on recent studies in PD.
 
This is an exploratory study. Therefore, a small sample size is appropriate. Any treatment effect could be used to power a future larger study.

SAFETY:	
Female subjects will undergo urine pregnancy testing if they are deemed to have any risk of being pregnant or becoming pregnant during the study. Baseline assessment of CBC, CMP, urinalysis, urine culture, and post-void residual will be conducted to address exclusion criteria.
 
Adverse Event Monitoring:
 

• This will be assessed at phone visits, visit 3 and 4 and continuously through phone contact and unscheduled visits as needed (see below)

• Additionally, post-void residual will be assessed at screening, visit 3, and visit 4 to screen for urinary retention as an adverse event.

 
Subjects will be monitored for adverse events throughout the trial. The occurrence of adverse events will be ascertained by observation, telephone monitoring if subjects call in, and by questioning by the investigator. Safety assessments will consist of monitoring and recording all adverse events, including serious adverse events. An adverse event is any undesirable sign, symptom or medical condition occurring after starting study drug (or therapy). Medical conditions/diseases present before starting study treatment are only considered adverse events if they worsen after starting study treatment.
 
Adverse events include adverse drug reactions, illness with onset during the study, exacerbations of pre-existing conditions or clinically significant changes in physical examination or significantly abnormal objective test findings. All adverse events will be recorded and graded as mild, moderate or severe by the principal investigator in accordance with general guidelines of clinical research.
 
A serious adverse event is an undesirable sign, symptom or medical condition which: 1. is fatal or life-threatening, 2. requires or prolongs hospitalization, 3. results in persistent or significant disability/incapacity, 4. constitutes a congenital anomaly or a birth defect, 5. is medically significant, in that it may jeopardize the subject and may require medical or surgical intervention to prevent one of the outcomes listed above. If any serious adverse events occur, the treatment status of the subject(s) may be revealed, as clinically indicated. Subjects who discontinue medication use

---

	will be followed for adverse events until reaching the termination of adverse events. The frequency of adverse events (AE) will be under continuous scrutiny during the observation with comparison to AE rates that have been recorded in published PD drug trials.
SCHEDULE OF EVENTS:	Refer to the Schedule of Events for timing of procedures
STUDY TIMELINE:	Start-up 2 months, period of enrollment 24 months, data analysis and final report 3 months

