## **7.4 Baseline-(Visit 2) -Treatment Initiation**

### **7.4.1 Confirmation of Eligibility**

Patients who are deemed eligible in the screening visit will go home to complete a 72-hour voiding diary and return for Visit 2 within 7-14 days after Visit 1. At visit 2, final eligibility will be confirmed by a review of the voiding diary. Subjects eligible to continue will have urinary urgency as evidenced by at least 8 episodes of urgency scores of 2 or greater in 72 hours AND will have urinary frequency as evidenced by having EITHER 8 or more episodes of micturition per 24 hours averaged over 72 hours OR 2 or more episodes of urinary incontinence in 72 hours. In addition to confirming eligibility, the diary scoring will provide the baseline values of mean daily OAB-SCS, number of micturitions per 24 hours, number of incontinence episodes per 24 hours, and mean volume per micturition.

In addition to the diary review, medications will be reviewed again to ensure stability of the PD medication regimen and absence of any prohibited medications. Vital signs will again be measured. At any visit, if a patient is found to have systolic blood pressure over 165, diastolic blood pressure over 100 or heart rate over 100, he or she will be withdrawn from the study.

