#### **7.4.3 Phone visit 1**

Phone visit 1 will take place 28-32 days after Visit 2 and no less than 72 hours prior to Visit 3. Patients will be prompted to resume the voiding diary for 72 hours. Screening for AEs will also take place during this phone visit.

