#### **7.5 Treatment titration**

##### **7.5.1 Visit 3**

Visit 3 will occur 32-40 days after Visit 2. This visit will include the same assessments as Visit 2, including review and entry of data in the voiding diary (mean daily OAB-SCS, number of micturitions per 24 hours, number of incontinence episodes per 24 hours, and mean volume per micturition). Visit 3 will also include review of current medication list, measurement of vital signs, PVR, OAB-q, NMSS, PPBC, and SGI-C. Screening for AEs will also take place during this visit. This will include assessment of symptoms of urinary tract infection and if, in the opinion of the study physician, urinalysis is indicated, dipstick will be performed with reflex to urine culture if positive. In pre-menopausal women, screening for pregnancy risk will be performed and if, in the opinion of the study physician, pregnancy testing is indicated, urine hCG will be measured.

In addition, at Visit 3, all patients who have tolerated mirabegron 25 mg daily or matching placebo (no adverse events on this dose) will be up-titrated to mirabegron 50 mg daily (for those in the active drug arm) or matching placebo (for those in the placebo arm). This will be dispensed as two 25-mg tablets or, for those in the placebo arm, two placebo tablets. Only

those without any AE on 25 mg daily or matching placebo will be eligible to increase the dose.

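### Phone Visit 1, the only stated trigger for the Visit 3 voiding diary, has two incompatible windows: 7-14 days after Visit 1 in the Synopsis, 28-32 days after Visit 2 in section 7.4.3

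*Protocol*

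**What the plan says.** The Protocol gives the timing of Phone Visit 1 twice.

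- Synopsis, Treatment Period: "Phone visit 1 at 7-14 days post visit 1".
- Section 7.4.3: "Phone visit 1 will take place 28-32 days after Visit 2 and no less than 72 hours prior to Visit 3".

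The surrounding schedule is as follows.

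- Section 7.4.1 has patients "return for Visit 2 within 7-14 days after Visit 1". The Synopsis agrees, giving one to two weeks from screening to baseline. Randomization and the start of treatment belong to Visit 2.
- Section 7.5.1: "Visit 3 will occur 32-40 days after Visit 2". The diary is reviewed and its data entered at that visit.
- Synopsis, Study Overview: "Voiding diaries (72-hr) will be utilized following the screening visit and phone visits 1 and 2". Section 7.1 repeats this.
- Section 7.4.3 says what the call is for: "Patients will be prompted to resume the voiding diary for 72 hours". It also includes an adverse event screen.
- The Synopsis lists "Change in mean daily OAB-SCS, Visit 3 vs. baseline" as a secondary outcome, together with Visit 3 comparisons of micturitions, incontinence episodes and volume per void, all taken from the diary.

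**The concern.** The protocol schedules three diaries: one after screening, one after Phone Visit 1 and one after Phone Visit 2. The first supplies baseline and the third supplies Visit 4. The diary for Visit 3 therefore depends wholly on when Phone Visit 1 takes place.

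The Synopsis puts that call in the same window as the baseline visit. If it were followed, the second diary would fall around baseline and nothing would prompt a diary near Visit 3. The four diary-based Visit 3 outcomes would lack data from the time point they are meant to describe. Visit 3 is also where up-titration is decided, so these are the only scheduled diary data from the end of the first dose period. They could not be collected afterwards.

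**Working it through.** No power or sample-size formula is involved; this is arithmetic on visit windows.

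**Inputs**
- Visit 2: days 7-14 after Visit 1 (section 7.4.1; Synopsis, one to two weeks).
- Phone Visit 1, Synopsis: days 7-14 after Visit 1.
- Phone Visit 1, section 7.4.3: days 28-32 after Visit 2.
- Visit 3: days 32-40 after Visit 2 (section 7.5.1).
- Diary length: 72 hours, or 3 days.

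**Step 1: both windows counted from Visit 1**
- Synopsis: days 7-14.
- Section 7.4.3: 7 + 28 = 35 to 14 + 32 = 46, so days 35-46.
- Smallest separation: 35 - 14 = 21 days. Largest: 46 - 7 = 39 days. The windows do not overlap.

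**Step 2: both windows counted from Visit 2**
- Synopsis: 7 - 14 = -7 to 14 - 7 = +7. The call may fall before, on or after the day of baseline.
- Section 7.4.3: +28 to +32.

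**Step 3: when the prompted diary would end**
- Synopsis: -7 + 3 = -4 to +7 + 3 = +10, in days from Visit 2.
- Time from the end of the diary to Visit 3: at least 32 - 10 = 22 days, at most 40 - (-4) = 44 days.
- Section 7.4.3: 28 + 3 = 31 to 32 + 3 = 35, next to a Visit 3 on days 32-40.

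**Step 4: can the section 7.4.3 window meet its own 72-hour condition?**
For a call on day 28, 29, 30, 31 or 32, the number of Visit 3 days in 32-40 that lie at least 3 days later is 9, 9, 8, 7 and 6. The total is 39 of 5 × 9 = 45 whole-day combinations, so the window is workable.

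**Step 5: could the Synopsis entry be a one-word slip?**
Reading its reference visit as Visit 2 gives days 7-14 after Visit 2, still 28 - 14 = 14 days short of the section 7.4.3 window. The diary would end by day 14 + 3 = 17, which is 32 - 17 = 15 days before the earliest Visit 3. The conflict remains.

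**Step 6: is the conflict confined to this call?**
Phone Visit 2 is 70-74 days after Visit 2 in both the Synopsis and section 7.5.2. Only Phone Visit 1 disagrees.

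**The case against.** The strongest reply is that nobody need be misled. The Synopsis itself sends the reader to the Schedule of Events for the timing of procedures. The body of the protocol is explicit and workable, and at a single site a missing diary would be noticed at the first Visit 3. This stands as a limit on likelihood: loss of the Visit 3 diary data is what follows if the Synopsis window is used, not a forecast. It does not remove the contradiction. The schedule (Appendix 14.1) is listed but not shown, so it cannot be assumed to settle the matter.

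A reader might also infer four stronger things that the document does not support.

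- *That the misplaced diary is always pre-treatment.* It is not. With Visit 2 on day 7 and the call on day 14, the call falls 7 days after baseline and the diary is kept on treatment. What holds in every case is that no diary comes from near Visit 3.
- *That up-titration would proceed without an adverse event check.* Section 7.5.1 has its own screen at Visit 3, and the Synopsis provides for ongoing contact and unscheduled visits. A mistimed call loses one contact.
- *That the primary result is at risk.* Visit 4 relies on Phone Visit 2, whose window is consistent.
- *That the diary must be finished 72 hours before Visit 3.* The condition in section 7.4.3 applies to the call. Applying it to diary completion would put the call about 72 + 72 = 144 hours before the visit, a stricter rule than the protocol states.

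**Conclusion.** This is an internal contradiction in a stated visit window, and no reading of the two passages reconciles them. The windows lie 21 to 39 days apart counted from Visit 1. If the Synopsis window were followed, the second diary would end at least 22 days before the earliest Visit 3. Four secondary outcomes would then have no data from that time point: mean daily OAB-SCS, micturitions, incontinence episodes and volume per void.

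The scope is limited. The primary endpoint and the clinic-based Visit 3 measures (OAB-q, NMSS, PPBC, SGI-C) do not depend on this call. The visit schedule in sections 7.4.3 to 7.6 is not itself in question.

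The conclusion assumes that Visit 2 falls within 7-14 days of Visit 1, that the diary starts on the day of the call, and that no other prompt for a Visit 3 diary exists in the schedule that is not shown. The correction should be made, but the point is of moderate weight.

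**What to change.** Reconcile the Treatment Period entry of the Synopsis with section 7.4.3, so that one Phone Visit 1 window appears in both and in the schedule of assessments (Appendix 14.1). The sponsor should state which window is intended. The agreed text should be checked against section 7.4.3's own condition that the call takes place no less than 72 hours before Visit 3, so that the 72-hour diary can be completed before that visit.

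The cost is a one-line correction in the next amendment and a check of the schedule and of any site document built from the Synopsis. Sample size, endpoints and analysis do not change.

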#### 4. LIST OF ABBREVIATIONS

AE	adverse event
ALT	alanine aminotransferase
ANCOVA	analysis of covariance
AST	aspartate aminotransferase
BP	blood pressure
CBC	complete blood count
CMP	complete metabolic panel
eGFR	estimated glomerular filtration rate
FDA	United States Food & Drug Administration
GCP	good clinical practice
HEENT	head, eyes, ears, nose, & throat
hCG	human chorionic gonadotropin
HR	heart rate
HY	Hoehn & Yahr
ICF	informed consent form
ICH	International Conference on Harmonisation
IRB	institutional review board
LEDD	levodopa-equivalent daily dose
LUTS	lower urinary tract symptoms
MDS	Movement Disorder Society
MDS-UPDRS	MDS' Unified Parkinson Disease Rating Scale
NMSS	non-motor symptom assessment scale for PD
OAB	overactive bladder
OAB-q	OAB questionnaire symptom severity scale
OAB-SCS	OAB symptom composite score
PD	Parkinson disease
PFE	pelvic floor exercise
PPBC	patient perception of bladder condition
PVR	post-void residual
RR	respiratory rate

---

SAE	serious AE
SIG-C	subject's global impression of change
U/A	urinalysis
UK	United Kingdom

## **5. INTRODUCTION (BACKGROUND AND RATIONALE)**

### **5.1 OAB Symptoms in PD**

Parkinson disease (PD) is the second most common neurodegenerative disease, behind only Alzheimer disease. Prevalence is estimated to be 0.3% of the general population and 1-2% of the population over the age of 60 (de Lau 2006, Kowal 2013). In 2005, 4 million people worldwide had PD, and that number is expected to more than double by 2030, to 8.7 million (Dorsey 2007). Estimates of prevalence in the United States vary from 340,000 (Dorsey 2007) to 630,000 (Kowal 2013). Prevalence in the US is expected to nearly double by 2030, with estimates ranging from 610,000 (Dorsey 2007) to 1.06 million (Kowal 2013) by 2030, and an estimate of 1.34 million by 2050 (Kowal 2013).

Urinary symptoms are common in PD. Prevalence estimates of lower urinary tract symptoms (LUTS) in PD range from 27% to 88% depending on severity threshold, screening tool, and sampling methods (Araki 2000b, Sammour 2009, Winge 2006, Winge 2012). LUTS include nocturia, urgency, frequency, and incontinence. LUTS increase morbidity (Balash 2005) and decrease quality of life (Araki 2000a, Sammour 2009) in PD.

Aside from the current study drug (Mirabegron), other FDA-approved oral medications for OAB have an anticholinergic mechanism of action. Patients with PD are especially sensitive to cognitive side effects of anticholinergic medications because they, by nature of their disease, have a significant cholinergic deficit. In addition, because of autonomic involvement in PD, these patients have a high rate of constipation, another symptom that may be significantly worsened by anticholinergic medications.

